9. RESEARCH METHODS

9.1. Study Design

This NI PASS will assess the incidence and risk of atrial fibrillation and supraventricular arrhythmia following receipt of ABRYSVO among adults 18 years of age and older in the VHA system from 31 May 2023 to 31 May 2026. All analyses will be conducted separately for individuals 18-59 years of age and for those at least 60 years of age. Pooled analysis using combined individual-level data from both age groups may be conducted (see Section

9.7 for further details). The following retrospective, longitudinal, observational cohort study designs will be implemented:

- The incidence of atrial fibrillation and supraventricular arrhythmia following administration of ABRYSVO will be assessed in the pre-specified post-vaccination period for each outcome (eg, 0-3 days for atrial fibrillation).
- An internal comparator cohort design (ie, contemporary control design) will serve as
 the primary study design and will compare the incidence of atrial fibrillation and
 supraventricular arrhythmia among those who received ABRYSVO to the incidence
 in two random samples of contemporaneous, index date-matched controls in the VHA
 system based on information recorded in the VHA database:
 - 1) Primary analysis individuals who were vaccinated with another vaccine (eg, influenza vaccine or Coronavirus Disease 19 (COVID-19) vaccine on the index date (eg, +/- 30 days); ie, contemporaneous vaccinated control cohort)
 - 2) Secondary analysis individuals who were not vaccinated with any vaccine on the index date but had at least one vaccination record in the year prior to the index date (ie, contemporaneous unvaccinated control cohort).

This will provide additional context for the interpretation for any potential observed excess risk as the controls will reflect the background rate of atrial fibrillation and supraventricular arrhythmia among vaccinated and unvaccinated individuals in the VHA population.

- A self-controlled risk interval (SCRI) design, which will serve as the secondary study
 design, will be used to compare the incidence of atrial fibrillation and
 supraventricular arrhythmia during the post-vaccination risk window (eg, 0-3 days
 following vaccination) to the post-vaccination control window (eg, 4-10 days
 following vaccination) among ABRYSVO vaccinated individuals within the VHA
 system.

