9.1.1. Primary Design - Internal Comparator Cohort Design (Contemporary Control Design)

To examine atrial fibrillation and supraventricular arrhythmia following ABRYSVO vaccination, days 0-3 will be used to define the risk interval, comprising a length of 4 days (ie, from the day of vaccination through the 3 days that follow, as only the date and not exact timing of vaccination will be known) for the primary analysis. This risk interval was selected based on post-marketing reports indicating atrial fibrillation onset less than one day after ABRYSVO administration, while accounting for a potential delay between the actual event

onset and when individuals seek care. As secondary analyses, days 0-1 comprising a length of 2 days (ie, the day of vaccination and the day following) will be used to define the risk interval, and days 0-30 comprising a length of 31 days (ie, the date of vaccination through the 30 days that follow) will be used to define the risk interval, similar to other studies that evaluated the risk for cardiac events (eg, myocarditis and pericarditis) to assess the safety profile of COVID-19 vaccines. ¹⁰⁻¹⁴ To reduce outcome misclassification, a confirmed case will require a diagnosis of atrial fibrillation (or supraventricular arrythmia) in the risk interval, with a confirmatory diagnosis within the subsequent 30 days for the primary and secondary analyses with different risk interval lengths (see Section 9.3.2).^{8,9}

Multivariable adjusted analyses will be performed comparing individuals who received ABRYSVO to individuals who received another vaccine (eg, influenza vaccine, COVID-19 vaccine, and other pre-specified vaccines such as shingles, hepatitis B listed in Section 9.3.3) at that point in time (+/- 30 days) [ie, contemporary vaccinated controls] in the primary analysis. The ABRYSVO cohort's index date will be defined as the date of vaccination with ABRYSVO. The vaccinated controls' index date will be defined as the date on which the individual received another vaccine that is within 30 days of a corresponding ABRYSVO vaccinee's vaccination date; these individuals can later receive ABRYSVO and enter the vaccination group if all eligibility criteria are met.

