9.2.1. Inclusion Criteria

Three cohorts will be defined for the main analyses.

- A. A cohort of individuals who received ABRYSVO will form the ABRYSVO cohort and must have:
 - A record for at least one dose of ABRYSVO in the study period from 31 May 2023 (or earliest date of vaccine availability for the indicated population) to 31 May 2026; the date of ABRYSVO vaccination will define the index date for this cohort
 - o No record of an RSV vaccine from a manufacturer other than Pfizer
- B. A cohort of individuals who did not receive ABRYSVO but received another vaccine will form the contemporary vaccinated control cohort and must have:
 - A record for another vaccine (eg, influenza vaccine, COVID-19 vaccine, and other pre-specified vaccines such as shingles, hepatitis B listed in Section 9.3.3) within 30 days of a corresponding ABRYSVO vaccinee's vaccination date; the control's index date will be the date of the control's non-RSV vaccine
 - No record for any RSV vaccine on the index date or in the baseline period (ie, 2 years prior to the index date)
 - Individuals in the vaccinated control cohort who go on to receive an RSV vaccine following their index date will be censored at the time of RSV vaccination. If the RSV vaccine is ABRYSVO, these individuals will contribute to the ABRYSVO cohort starting from the date of ABRYSVO receipt.
- C. A cohort of individuals who did not receive ABRYSVO or another vaccine on the index date but had at least one vaccination record in the year prior to the index date will form the contemporary unvaccinated control cohort and must have:
 - No record for any RSV vaccine on or within 30 days of the index date or in the baseline period (ie, 2 years prior to the index date)

- No record for any other vaccine (eg, those listed in Section 9.3.3) on or within 30 days of the index date
 - This cohort will be assigned an index date matched to a corresponding ABRYSVO vaccinee's vaccination date. If the vaccination is associated with a healthcare encounter (ie, inpatient [IP] or outpatient [OP] visit), the unvaccinated control will be required to have a healthcare encounter within 30 days of the assigned index date, and the date of the healthcare encounter will be set as the index date for the unvaccinated control.

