 - Individuals in the unvaccinated control cohort who go on to receive an RSV vaccine following their index date will be censored at the time of RSV vaccination. If the RSV vaccine is ABRYSVO, these individuals will contribute to the ABRYSVO cohort starting from the date of ABRYSVO receipt.
- o Regular use of preventive medical care, defined as at least one vaccination record between 365 to 31 days prior to the index date.

In addition, individuals in all cohorts must meet the following inclusion criteria to be eligible for the study:

- At least 2 years of continuous enrollment in (ie, no disenrollment from) VHA benefits (ie, the baseline period) prior to the index date
- Complete follow-up (ie, no disenrollment from VHA benefits, death, or receipt of RSV vaccination [for controls who may later receive any RSV vaccine only]) during the risk interval and confirmatory diagnosis window (eg, 34 days of complete follow-up for 0-3 days primary risk interval plus 30-day confirmatory diagnosis window; or 32 days or 61 days for secondary analysis with 0-1 days and 0-30 days risk intervals plus 30-day confirmatory diagnosis window, respectively).

Based on age on the index date, eligible individuals will be further classified into the following two age groups with the following additional inclusion criteria:

- 18-59 years old age group
 - o 18-59 years of age on the index date
 - o For individuals in cohorts B and C, a record for specific conditions that increase the risk for severe RSV as defined by the CDC during the baseline period, identified as those with chronic cardiovascular disease, chronic lung or respiratory disease, end-stage renal disease or dependence on hemodialysis or other renal replacement therapy, diabetes mellitus with complications, neurologic or neuromuscular conditions causing impaired airway clearance or respiratory muscle weakness, chronic liver disease, chronic hematologic

conditions, severe obesity, moderate or severe immune compromise, residence in a nursing home, or other chronic medical conditions or risk factors that a health care provider determines would increase the risk for severe disease due to viral respiratory infection (eg, frailty); list of conditions may be updated to align with the most current CDC definition at the time of data analysis¹⁹

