9.2.3. Subgroups

Safety surveillance may be conducted for subgroups of interest as applicable to each age group, including, but not limited to the ones described below.

The following subgroups will be analyzed for the 18-59 years old age group and the 60 years and older age group:

- Individuals in VA priority group 1; These individuals have either the highest levels of service connected disability (≥50% disabling), are considered unemployable, or have received the medal of honor. Individuals categorized as priority group 1 are the highest priority for VHA care. This will ensure that the individual is more likely to receive all of their care from a VA facility;
- Females enrolled in the VHA (pending sufficient sample size);

• Individuals with co-administration with other vaccines (ie, influenza vaccine, COVID-19 vaccine, or other pre-specified vaccines [eg, shingles, hepatitis B] listed in Section 9.3.3) on the same day.¹⁸

The following subgroups will be analyzed for the 60 years and older age group only:

- Individuals with specific conditions that increase the risk for severe RSV as defined by the CDC during the baseline period; list of conditions may be updated to align with the most current CDC definition at the time of data analysis (see Section 9.2.1);
- Different age groups defined by age on the index date, eg, 60 to 69 years, 70 to 79 years, ≥80 years;
- Individuals enrolled in the VHA with dual coverage who are also identified in the Centers for Medicare & Medicaid Services (CMS) Medicare administrative claims data, which will be linked to the Corporate Data Warehouse (CDW) to supplement the data for a more complete evaluation of healthcare encounters.

Additional subgroups of interest may be assessed as additional information becomes available from ongoing clinical trials, Vaccine Adverse Event Reporting System (VAERS), and other sources that will inform the ABRYSVO safety profile.

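### On its natural reading, the unvaccinated-control criterion excludes controls for a non-RSV vaccine given in the 30 days after index, a condition not set for ABRYSVO recipients; the size and direction of the resulting bias are unknown

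*Protocol*

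**What the plan says.** Section 9.1 introduces the secondary comparison group as "individuals who were not vaccinated with any vaccine on the index date but had at least one vaccination record in the year prior", and the abstract (Section 4) says the same. Section 9.2.1, cohort C, adds a stricter criterion: "No record for any other vaccine (eg, those listed in Section 9.3.3) on or within 30 days of the index date". The companion criterion for RSV vaccines reads "No record for any RSV vaccine on or within 30 days of the index date or in the baseline period", the baseline period being the 2 years before index.

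For ABRYSVO recipients (cohort A), Section 9.2.1 asks for "A record for at least one dose of ABRYSVO in the study period from 31 May 2023" and no RSV vaccine from another manufacturer. It sets no condition on non-RSV vaccines before or after index. Section 9.2.3 lists "Individuals with co-administration with other vaccines" as a subgroup, so other vaccines are expected in that arm.

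For later RSV vaccination there is an explicit rule: "Individuals in the unvaccinated control cohort who go on to receive an RSV vaccine following their index date will be censored at the time". The censoring events in Section 9.1.1 are disenrollment, death, RSV vaccination in controls, and the end of the risk window. Later non-RSV vaccination is not among them.

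**The concern.** Eligibility for a comparison cohort should be decidable at index. If the 30-day window runs forward as well as back, whether a person counts as an unvaccinated control is known only on day 30, and the outcome may have influenced it. The primary risk interval is days 0-3, so most of the forward window follows it. For the secondary 0-30 day interval, the forward window covers 30 of its 31 days. Because later non-RSV vaccination is not a censoring event, in cohort C it acts as a retrospective exclusion, and in one arm only.

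The ATT weights in Section 9.7.2.2 condition on characteristics at the index date, so they cannot undo selection on something that happens afterwards. At stake is the background rate among unvaccinated people, which Section 9.1 says these controls are there to provide.

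**Working it through.** **Which way does the window run?** The protocol never says 'after' for this criterion. Three places bear on it.

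- The RSV criterion for the same cohort uses the same phrase in addition to a 2-year look-back. A 30-day look-back would already lie inside those 2 years, so the phrase adds something beyond the index date only if it reaches past it.
- Where the protocol wants a look-back for this cohort, it says so: "Regular use of preventive medical care, defined as at least one vaccination record between 365 to 31 days prior to the index date".
- The 30-day window for vaccinated controls in Section 9.1.1 is written with a plus-or-minus sign.

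Two-sided is therefore the natural reading, though not an explicit one.

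**The plan's own figure.** Section 9.5.1 and Table 2 give 37,444 vaccinees aged 60 or older at 4:1 to detect a ratio of 2.0 (33.9 events per 1,000 person-years, 4-day interval, one-sided alpha 0.05, 80% power). With μ = 0.0339 × 4/365 = 0.0003715 and (1.645 + 0.842)² = 6.183 (from unrounded normal quantiles):

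n = 6.183 × (2μ + μ/4) / μ² = 6.183 × 2.25/μ ≈ 37,444.

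The same formula gives 116,493 for a ratio of 1.5. The plan's figures reproduce and are not in dispute.

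**Effect of the forward exclusion.** Let q be the share of event-free controls given a non-RSV vaccine in days 1-30, and r the same probability in atrial fibrillation cases relative to event-free controls. The rule keeps (1-q) of event-free controls and (1-qr) of cases. Because events are rare (μ is about 0.0004), the control rate is multiplied by

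f = (1-qr)/(1-q), and the observed hazard ratio is the true hazard ratio divided by f.

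**Power.** At n = 37,444 and a true ratio of 2.0, the plan's formula gives Φ[(2-f) × √(nμ/(2 + f/4)) - 1.645], with nμ = 13.91. At f = 1 this is 80%.

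Neither q nor r is in the protocol. The values below are assumptions chosen to span both directions.

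| q | r | f | true 2.0 reads as | true 1.0 reads as | power at 37,444 |
|---|---|---|---|---|---|
| 0.1 | 0.5 | 0.95/0.90 = 1.056 | 1.89 | 0.95 | 76% |
| 0.1 | 1.5 | 0.85/0.90 = 0.944 | 2.12 | 1.06 | 84% |
| 0.2 | 0 | 1.00/0.80 = 1.250 | 1.60 | 0.80 | 58% |
| 0.2 | 0.5 | 0.90/0.80 = 1.125 | 1.78 | 0.89 | 70% |
| 0.2 | 1 | 0.80/0.80 = 1.000 | 2.00 | 1.00 | 80% |
| 0.2 | 1.5 | 0.70/0.80 = 0.875 | 2.29 | 1.14 | 88% |
| 0.3 | 0.5 | 0.85/0.70 = 1.214 | 1.65 | 0.82 | 61% |
| 0.3 | 1.5 | 0.55/0.70 = 0.786 | 2.55 | 1.27 | 92% |

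The higher power when r exceeds 1 is not a gain: the same distortion makes a null effect look harmful.

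**The case against.** **The window may be meant as a look-back.** The requirement of an earlier vaccination stops at day 31 before index, which fits a vaccine-free 30 days before index and needs nothing after it. In addition, if the RSV criterion barred RSV vaccination for 30 days after index, censoring cohort C at RSV vaccination could never act within any planned risk interval. The first point stands as evidence that a look-back was at least part of the intent. The second is weaker, because Section 9.2.1 separately requires complete follow-up free of RSV vaccination through the risk and confirmation windows, and that alone leaves the censoring rule idle. What remains is wording that does not state its direction and that most naturally reads as two-sided.

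**A reader might infer that the rule inflates the control rate and hides harm.** That needs r below 1. It is plausible that someone with acute atrial fibrillation puts off a routine vaccine. But every counted case needs a second diagnosis within 30 days, and that extra contact is also an occasion to vaccinate, which would push r above 1 and the hazard ratio upward. The protocol settles neither.

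**A reader might also infer a flat contradiction with Sections 4 and 9.1, or damage to the primary analysis.** The shorter definitions can be read as summaries of the detailed criteria; cohort C's own lead-in repeats the index-date wording before adding to it. The primary comparison uses vaccinated controls, to whom this criterion does not apply.

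**Conclusion.** The selection defect is real on the natural reading. Control eligibility depends on events after index, ABRYSVO recipients have no matching condition, and baseline weighting cannot repair it. It is confined to the secondary, unvaccinated comparison.

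Its size rests entirely on assumed q and r. For q from 0.05 to 0.3 and r from 0.5 to 1.5, f runs from 0.79 to 1.21, so a true hazard ratio of 2.0 would read anywhere from 2.55 down to 1.65. Controls must have a vaccination record in the preceding year, so q is unlikely to be negligible. Bias toward no harm is the likelier direction if acute illness delays vaccination, but it is not established. A bias of unknown sign is reason enough to remove the rule. If only a look-back was intended, the same edit settles the point.

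**What to change.** In Section 9.2.1, reword the cohort C criterion to: *no record of any other vaccine on the index date or in the 30 days before it*. Eligibility then uses only information available at index.

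Add one rule for non-RSV vaccines given after index and apply it identically to ABRYSVO recipients and unvaccinated controls: for example, ignore them in the main analysis and censor at them in both arms as a sensitivity analysis. Censoring controls alone would create a new asymmetry between arms. Any such censoring should end time at risk for a new event but leave the 30-day confirmation window intact. Otherwise a control with a first code on day 2, another vaccine on day 15 and a confirmatory code on day 20 would be lost as a case.

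Align the definitions in Sections 4 and 9.1 with this wording.

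The cost is a few sentences and no new data, and more controls become eligible. The downside is that some controls will receive another vaccine during the 0-30 day interval, so they are unvaccinated at index but not throughout; the two-arm censoring analysis shows how much that matters.

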As a secondary analysis, individuals who received ABRYSVO will be compared to individuals not receiving any vaccinations at that point in time but had at least one vaccination record in the year prior to the index date (ie, contemporary unvaccinated controls). The unvaccinated controls will be assigned an index date matched to a corresponding ABRYSVO vaccinee's vaccination date; these individuals can later receive ABRYSVO and enter the vaccination group if all eligibility criteria are met. To address possible selection bias due to health seeking behaviors, the unvaccinated controls will be randomly selected from a population of patients who have regular use of preventive medical care within the VHA system, defined as at least one vaccination record in the year prior to the index date. The index date for the contemporary unvaccinated controls will be selected based on the observed index dates in the vaccinated cohort. If ABRYSVO vaccination is associated with a regular healthcare encounter, the contemporary unvaccinated control will be required to have an encounter within 30 days of the assigned index date, and the date of encounter will be set as the index date to ensure comparability of covariate measurement.

In the primary analysis, the ABRYSVO vaccinated, contemporary vaccinated control, and contemporary unvaccinated control cohorts will be followed for up to 34 days post-index (ie, 0-3 day risk interval plus 30-day diagnosis confirmation window) to assess and confirm the occurrence of atrial fibrillation and supraventricular arrhythmia. In secondary analyses, the cohorts will be followed up to 32 days post-index (ie, 0-1 day risk interval plus 30-day diagnosis confirmation window) and up to 61 days post-index (ie, 0-30 day risk interval plus 30-day diagnosis confirmation window). Individuals will be censored upon the earliest occurrence of disenrollment, death, date of RSV vaccination (for controls who later receive any RSV vaccine only), or end of the risk window. The date of the first atrial fibrillation (or supraventricular arrythmia) case will be considered date of onset.

[figure not shown]

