9.3.2. Outcomes

The study's primary outcome, new onset atrial fibrillation, will be identified by a diagnosis code for atrial fibrillation in any setting during the 0-3 day risk interval (or 0-1 day or 0-30 day risk interval for secondary analysis), or corresponding control interval, followed by a confirmatory diagnosis within 30 days after the initial diagnosis. To be considered an incident case, no diagnosis for atrial fibrillation or other supraventricular arrhythmia should be observed in the 2 years prior to the index date (ie, "clean window," the occurrence-free

baseline period used to define incident outcomes during which individuals enter the study cohort only if the safety event did not occur during this period).^{8,9}

The secondary outcome of the study will be new onset supraventricular arrhythmia, including atrial fibrillation, and will be identified in the same manner as the primary outcome (ie, a diagnosis code for the event in any setting during the risk interval, or control interval, followed by a confirmatory diagnosis within 30 days after the initial diagnosis, and no diagnosis code for atrial fibrillation or other supraventricular arrhythmia in the 2-year clean window).

The study outcomes and operational definitions of the outcome variables based on International Classification of Diseases, Tenth Revision, Clinical Modification (ICD-10-CM) diagnosis codes are outlined in Table 1. ICD-10-CM diagnosis codes occurring in any position (ie, primary or secondary) in OP (including emergency department [ED]) and/or IP settings will be used to identify safety events.

Table 1. Safety events, including outcome algorithms and risk and control intervals

Safety Event	Operational Definition Defined by the presence of any of the following ICD- 10-CM codes (inclusive):	Setting (IP, OP)	Clean Window	Risk Interval (Days)	Post- Vaccination Control Interval for SCRI Design (Days)
Atrial fibrillation (primary outcome) ⁵⁰	 I48.0, Paroxysmal atrial fibrillation I48.19, Other persistent atrial fibrillation I48.20, Chronic atrial fibrillation, unspecified I48.91, Unspecified atrial fibrillation 	IP or OP	2 years	Primary: 0-3 Secondary : 0-1 and 0-30	Primary: 4-10 Secondary: 2-8 and 31- 61

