Supraventricular arrhythmia, including atrial fibrillation (secondary outcome) ⁵⁰	Paroxysmal tachycardia I47.0, Re-entry ventricular arrhythmia I47.10, Supraventricular tachycardia, unspecified I47.11, Inappropriate sinus tachycardia I47.19, Other supraventricular tachycardia I47.9, Paroxysmal tachycardia, unspecified Atrial fibrillation:	IP or OP	2 years	Primary: 0-3 Secondary : 0-1 and 0-30	Primary: 4-10 Secondary: 2-8 and 31- 61

Table 1. Safety events, including outcome algorithms and risk and control intervals

Safety Event	Operational Definition Defined by the presence of any of the following ICD- 10-CM codes (inclusive):	Setting (IP, OP)	Clean Window	Risk Interval (Days)	Post- Vaccination Control Interval for SCRI Design (Days)
	See "Atrial fibrillation (primary outcome)" above				
	 Atrial flutter: 148.3, Atrial flutter 148.4, Atypical atrial flutter 148.92, Unspecified atrial flutter 				
	Other cardiac arrhythmia: • I49.1, Atrial premature depolarization • I49.5, Sick sinus syndrome • I49.8, Other specified cardiac arrhythmias including Brugada syndrome, coronary sinus rhythm disorder, ectopic rhythm disorder, nodal rhythm disorder				

Abbreviations: ICD-10-CM, International Classification of Diseases, Tenth Revision, Clinical Modification; IP, inpatient; OP, outpatient.

The risk intervals were selected based on published literature and biological plausibility. ¹⁰⁻¹⁷ A safety event will be counted if it can be assigned to 1) the risk interval following ABRYSVO, 2) the post-vaccination control interval (SCRI design), or 3) risk interval for the contemporary vaccinated or unvaccinated controls. The risk intervals for outcome evaluation for contemporary vaccinated or unvaccinated controls will be the same as for individuals who received ABRYSVO.

Events outside these intervals will not be counted. Only the individual's first instance of a safety event following the 2-year clean window will be included; this means that if a safety

event is identified but diagnosis codes corresponding to the safety event are also observed during the clean window, it will not be counted to rule out pre-existing events.

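### In the secondary unvaccinated comparison, a control's index date can be moved onto the control's own first AF visit, which raises the control rate and biases the hazard ratio downward by an amount the protocol does not determine

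*Protocol*

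**What the plan says.** Protocol Section 9.2.1 (cohort C) gives each unvaccinated control an index date matched to a vaccinee's vaccination date, then adds a condition: "If the vaccination is associated with a healthcare encounter (ie, inpatient [IP] or outpatient [OP] visit"). Where the condition is met, the control must have had some encounter no more than 30 days away from the date first assigned. That encounter then supplies the new time zero: "and the date of the healthcare encounter will be set as the index date for the unvaccinated control". Section 9.1.1 repeats the rule and gives its purpose: "the date of encounter will be set as the index date to ensure comparability of covariate measurement". Neither section restricts the reason for the control's encounter or its setting, or says which encounter to take when there are several. In Section 9.1.1 the word regular describes the vaccinee's encounter, not the control's.

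Four other provisions bear on this:
- Section 9.1.1 defines the primary risk interval as days 0-3, "from the day of vaccination through the 3 days that follow".
- Section 9.3.2: "The risk intervals for outcome evaluation for contemporary vaccinated or unvaccinated controls will be the same as for individuals who received ABRYSVO".
- Section 9.3.2: the primary outcome "will be identified by a diagnosis code for atrial fibrillation in any setting during the 0-3 day risk interval", with a confirmatory code within 30 days.
- Sections 9.2.2 and 9.3.2 exclude AF or other supraventricular arrhythmia only in the 2 years before the index date. The index date itself is not screened.

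Sections 9.1 and 9.1.1 label the unvaccinated comparison a secondary analysis.

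**The concern.** A vaccinee's day 0 is fixed by receipt of the vaccine. A re-indexed control's day 0 is fixed by having sought care, for any reason, including a first episode of AF. Such a control passes the 2-year clean window, has the AF visit as day 0 and, once a second code follows, is a case. If a later encounter of the same person is chosen instead, the AF falls in the baseline period and the person is excluded. Time zero in the control cohort can thus depend on the outcome.

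Section 9.1 says the controls are there to show the background rate. Under this rule they would show more than that, so a true increase after ABRYSVO would be understated. For a safety study that is the unfavourable direction.

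The planned safeguards do not correct it. ATT weighting (Section 9.7.2.2) balances baseline covariates and cannot repair the definition of time zero. Chart adjudication (Section 9.7.2.4) covers only ABRYSVO recipients. Negative control outcomes (Section 9.7.4.1) may reveal a bias but do not remove it.

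**Working it through.** **Inputs from the protocol.** Background AF rate at age 60 and over: 33.9 per 1,000 person-years (Section 9.5.1). Primary risk interval: 4 days. Search window: within 30 days, read as 30 days either side, so 61 days. **Assumed, because the protocol gives no figure:** p, the chance that a control whose first AF visit falls in the window has that visit chosen as index; the share s of controls re-indexed; how often controls have other encounters.

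**Anchor on the plan's own figure.** The 4-day risk is p0 = 0.0339 × 4/365 = 0.0003715. For IRR 2.0 and 4:1 matching, n = (1.645 + 0.842)² × (2p0 + p0/4)/p0² = 6.183 × 2.25/0.0003715, or about 37,444. This matches Table 2, so the rate and interval are used as the protocol uses them. Table 2 is not in question.

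**Control-rate inflation if every control is re-indexed.**
- Risk of a first AF code in the window: 0.0339 × 61/365 = 0.005665.
- Ratio to the 4-day risk: 61/4 = 15.25.
- Day-0 cases contribute 15.25p and days 1-3 contribute 3/4, so inflation k = 15.25p + 0.75.
- Check: an index date unrelated to AF has p = 1/61, giving 0.25 + 0.75 = 1.0.
- p = 5%: 0.76 + 0.75 = 1.5-fold.
- p = 10%: 1.53 + 0.75 = 2.3-fold.
- k reaches 2 at p = (2 − 0.75)/15.25 = 8.2%.

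**Other risk intervals, at p = 10%.** Days 0-1: 30.5p + 0.5 = 3.6-fold. Days 0-30: (61/31)p + 30/31 = 1.2-fold. The short intervals are the sensitive ones.

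**Only some controls re-indexed.** Inflation is 1 + s(k − 1). At p = 10% (k = 2.275): 1.64-fold for s = 50% and 1.32-fold for s = 25%.

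**From control rate to hazard ratio.** AF found at vaccinees' own day-0 encounters counts too. Suppose a share f of first AF codes comes from visits made because of AF, and the rest arises at routine visits, enriched equally in both cohorts. The net bias is then k/(f + (1 − f)k). With f = 50% (assumed) and all controls re-indexed:
- p = 5%: 1.5125/(0.5 + 0.756) = 1.20, so a true ratio of 2 reads 2/1.20 = 1.66.
- p = 10%: 2.275/(0.5 + 1.1375) = 1.39, so a true ratio of 2 reads 2/1.39 = 1.44.

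**What p could be.** A simulation of the rule placed AF uniformly over the window, with one follow-up visit within 30 days of AF and all controls re-indexed. It took an assumed 1, 2, 4, 8 or 15 other encounters per 61 days. Control-rate inflation was 10.8, 6.1, 3.7, 2.3 and 1.7-fold when the encounter was picked at random, and 10.5, 5.8, 3.4, 2.2 and 1.5-fold when the closest was taken. Reading the window as forward only (0 to +30 days) gave 12.1, 3.7 and 2.3-fold at 1, 4 and 8 encounters (random pick). The range shows how far the size depends on inputs the protocol does not give.

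**The case against.** The strongest reply concerns scope and size, and most of it stands.

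- Only a secondary comparison is touched. The primary analysis indexes vaccinated controls on their own vaccine date, the SCRI uses vaccinees only, and the primary objective is AF incidence after ABRYSVO. This stands.
- The rule is conditional on the matched vaccination being tied to an encounter. Section 9.7.1 lists pharmacy among the vaccination settings, so some controls keep their assigned date. This stands and lowers the inflation.
- A reader might divide 2 by the control inflation and infer that a true hazard ratio of 2 would appear as 0.88 at p = 10%, a harmful vaccine looking protective. The documents do not support that. It re-indexes every control and holds vaccinees at exactly twice background, although AF coded at their own day-0 encounters also counts.
- A reader might also take a several-fold distortion as established. It is not: visit frequency, the choice of encounter and the share re-indexed are all absent from the protocol.
- Which of several encounters to take could be left to the SAP. That is fair for the tie-break. It does not answer the main point: the protocol itself admits any inpatient or outpatient encounter and counts the index day.
- Negative control outcomes could expose the problem, particularly an acute one such as appendicitis, which Section 9.7.4.1 mentions. That would be detection, not correction.

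**Conclusion.** The flaw is real and lies in a stated rule, not in missing detail. In the secondary unvaccinated comparison, a control's first AF visit can set time zero and count as an event. The direction follows from the text: the control rate goes up and the hazard ratio goes down.

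The size is not fixed by the protocol. With all controls re-indexed and a 61-day window, the control rate rises about 1.5-fold at an assumed p of 5% and 2.3-fold at 10%. It rises less if only some controls are re-indexed, and the hazard-ratio bias is smaller than the rate inflation. Under the illustrative 50% split it is about 1.2 to 1.4-fold: attenuation of a true doubling, not a reversal. The primary vaccinated-control analysis, the SCRI and the Table 2 sample sizes are unaffected.

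**What to change.** In Sections 9.1.1 and 9.2.1 (cohort C), require that the control's index encounter:
- is of the same care setting as the matched vaccination encounter, with no ED or inpatient encounter unless the vaccinee's was one; and
- is the one nearest the assigned date, chosen without regard to its diagnosis codes.

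The setting restriction should do most of the work. In the simulation, taking the nearest encounter alone barely lowered the inflation (3.4 against 3.7-fold at 4 other encounters), though it does fix an otherwise open choice. AF first coded at an outpatient visit can still set the index date. So add a sensitivity analysis of this comparison that, in both cohorts, does not count AF first coded at the index encounter.

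That exclusion should not move into the main analysis. Section 9.1.1 bases the risk interval on reports of onset less than one day after vaccination, and dropping index-encounter codes could discard true events.

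The cost is some loss of eligible controls and one extra analysis. The sensitivity analysis may itself miss true AF arising after vaccination within the same encounter, and should be read with that in mind.
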